5. SUBJECT ENROLLMENT

Before subjects may be entered into the study, Amgen requires a copy of the site's written institutional review board/independent ethics committee (IRB/IEC) approval of the protocol, informed consent form and assent form if applicable. All subjects or legally acceptable representatives must personally sign and date the consent and assent form (if applicable) before study-specific procedures are performed. Adverse events are only reported for subjects enrolled in the study. Subjects are considered enrolled once they have been entered through the IVRS and have received their first dose of IP.

Product: Romiplostim
Protocol Number: 20101221
Date: 15 August 2014

Page 25 of 69

All subjects who enter into the screening period for the study (entry is defined as the point at which informed consent is signed) will receive a unique subject identification number before any study procedures are performed. This number will be used to identify the subject throughout the clinical study and must be used on all study documentation related to that subject.

The subject identification number must remain constant throughout the entire clinical study; it must not be changed at the time of rescreening or enrollment.

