7.5 Screening

The screening period begins on the date that the subject (and/or the subject's legally authorized representative) signs the IRB/IEC-approved informed consent form and continues until the date of enrollment. Procedures that are part of routine care are not considered study-specific procedures. All subjects will be screened for eligibility before enrollment.

The following screening procedures must be completed within 4 weeks before the day of first dose of romiplostim:

- informed consent (and assent if required by IRB/IEC)
- confirmation of ITP diagnosis
- ITP and medical history
- physical exam as per standard of care including weight and vital signs. Physical examination findings should be recorded on the medical history or adverse event eCRF
- concomitant medications
- central lab CBC with differential and blood chemistry
- confirmation of one local lab platelet count $\leq 30 \times 10^9/L$ and/or documentation of bleeding that was uncontrolled with conventional therapies for ITP
- local lab urine or serum pregnancy test for female subjects of child-bearing potential (defined as having first menses)
- serious adverse events that occurred after the signing of informed consent

If subjects do not successfully complete screening within 4 weeks after initial informed consent, their screen failure will be registered in the IVRS. Subjects who fail screening will be allowed to re-screen. Subjects who rescreen must repeat relevant screening procedures within the new 4-week screening window. If the subject's screening platelet count is $> 30 \times 10^9/L$ without evidence of uncontrolled bleeding with conventional

Product: Romiplostim
Protocol Number: 20101221
Date: 15 August 2014

Page 38 of 69

therapies upon initial assessment the site may reassess the platelet count during the 4-week screening period without registration of screen-failure or re-consenting the subject.

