9.2 Reporting of Adverse Events

9.2.1 Reporting Procedures for Adverse Events That do not Meet Serious Criteria

The investigator is responsible for ensuring that all adverse events observed by the investigator or reported by the subject that occur after first dose of investigational product through the end of treatment period are reported using the applicable eCRF (eg, Adverse Event Summary CRF).

Because all subjects who enter the study will be diagnosed with ITP according to the ASH guidelines, ITP should not be reported as an adverse event during the conduct of the study.

The investigator must assign the following adverse event attributes:

- adverse event diagnosis or syndrome(s), if known (if not known, signs or symptoms)
- dates of onset and resolution (if resolved)

- severity
- assessment of relatedness to romiplostim
- action taken

The adverse event severity grading scale used will be the Common Terminology Criteria for Adverse Events (CTCAE) version 3.0 grading scale. The severity grading scale used in this study is described in [Appendix A](#).

The investigator must assess whether the adverse event is possibly related to the romiplostim. This relationship is indicated by a “yes” or “no” response to the question: Is there a reasonable possibility that the event may have been caused by the romiplostim?

The investigator must assess whether the adverse event is possibly related to any study-mandated activity (eg, administration of investigational product, protocol-required therapies, device(s) and/or procedure (including any screening procedure(s))). This relationship is indicated by a “yes” or “no” response to the question: “Is there a reasonable possibility that the event may have been caused by a study activity (eg, administration of investigational product, protocol-required therapies, device(s)), and/or procedure?”

The investigator is responsible for reviewing laboratory test results and determining whether an abnormal value in an individual study subject represents a clinically significant change from the subject’s baseline values. In general, abnormal laboratory findings without clinical significance (based on the investigator’s judgment) are not to be recorded as adverse events. However, laboratory value changes that require treatment or adjustment in current therapy are considered adverse events. Where applicable, clinical sequelae (not the laboratory abnormality) are to be recorded as the adverse event.

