9.2.2 Reporting Procedures for Serious Adverse Events

The investigator is responsible for ensuring that all serious adverse events observed by the investigator or reported by the subject that occur after signing of the informed consent through 30 days after last dose of IP (for subjects who have sustained platelet responses and never resume IP after sustained response during the trial); or the later of the EOT and EOS visits, are recorded in the subject’s medical record and are submitted

Product: Romiplostim
Protocol Number: 20101221
Date: 15 August 2014

Page 44 of 69

to Amgen. All serious adverse events must be submitted to Amgen within 24 hours following the investigator's knowledge of the event via the applicable CRF.

After the protocol-required reporting period defined above, the investigator does not need to actively monitor subjects for serious adverse events. However, if the investigator becomes aware of a serious adverse event after this protocol-required reporting period, the investigator will report the event to Amgen within 24 hours following the investigator's knowledge of the event. Serious adverse events reported outside of the protocol-required reporting period will be captured within the safety database as clinical trial cases for the purposes of expedited reporting.

If the electronic data capture (EDC) system is unavailable to the site staff to report the Serious Adverse Event, the information is to be reported to Amgen via an electronic Serious Adverse Event (eSAE) Contingency Report Form within 24 hours of the Investigator's knowledge of the event. See [Appendix A](#) for a sample of the Serious Adverse Event Worksheet/electronic Serious Adverse Event Contingency Report Form. For EDC studies where the first notification of a Serious Adverse Event is reported to Amgen via the eSerious Adverse Event Contingency Report Form, the data must be entered into the EDC system when the system is again available

The investigator must assess whether the serious adverse event is possibly related to any study-mandated activity or procedure. This relationship is indicated by a "yes" or "no" response to the question: "Is there a reasonable possibility that the event may have been caused by a study activity/procedure"?

The investigator is expected to follow reported serious adverse events until stabilization or reversibility.

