Add new section 7.1.4 Bone Marrow Biopsy	Not applicable	
Bone Marrow Biopsy
 
For the protocol supplement, a baseline bone marrow biopsy and aspirate is required to determine eligibility; central laboratory evaluation is required prior to first dose of romiplostim. A baseline bone marrow biopsy can be either a bone marrow biopsy within 1 year prior to the planned first dose of romiplostim (with available bone marrow tissue block or a minimum of 5 unstained, evaluable histological slides to send to a central laboratory) or a pre-treatment bone marrow biopsy and aspirate within 3 weeks prior to planned first dose of romiplostim.
 
A repeat bone marrow biopsy and aspirate is required at Year 1 or Year 2 (\pm 4 week window) depending on the cohort assignment. A bone marrow biopsy and aspirate should be obtained for discontinued subjects who have not yet had a cohort-defined bone marrow biopsy performed.
 
Should collagen be detected in any subjects during the course of the study, study drug will be discontinued and the subject will undergo an EOT visit. A repeat bone marrow biopsy will be required 12 weeks later at the EOS visit (+ 2 week window) for subjects who are withdrawn from the study due to the presence of collagen.
 
Subjects who have a change to grade 3 reticulin, per central laboratory evaluation of a bone marrow biopsy, will undergo a repeat bone marrow biopsy 12 weeks after their last dose of romiplostim at the EOS visit (+ 2 week window).
 
Subjects who are considered non-responders and will be discontinued from the study will require a bone marrow biopsy and aspirate sample to be taken at the EOT visit (+ 2 week window). A repeat bone marrow biopsy will also be required 12 weeks later at EOS visit (+ 2 week window) for non-responders who have a change to grade 3 reticulin or collagen, per central laboratory evaluation of a bone marrow biopsy.
 
Bone marrow biopsies and aspirates where applicable, will be sent to a central laboratory for reticulin and collagen staining and analysis. Refer to Central Laboratory Manual for instructions on collection, preparation, storage, and shipment of samples. The modified Bauermeister Scale (Bauermeister, 1971) will be used for this study. Subjects with a reticulin grade of 0, 1, 2, or 3 will be eligible for this study.

Table 1. Summary of Changes

Protocol Section	Text in Protocol	Text For the EU, Switzerland, and Turkey

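### Non-serious harm from the supplement's screening and 12-week end-of-study marrow biopsies falls outside the adverse-event window, and Section 5 contradicts the serious-event rules for children never dosed

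*Protocol*

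**What the plan says.** **Non-serious events.** Protocol 9.2.1 covers those "that occur after first dose of investigational product through the end of treatment period are reported using the applicable eCRF". Table 2 follows it: the adverse-event row is blank at screening and at EOS, and marked from week 1 to the end-of-treatment (EOT) visit. Section 9.2.1 also asks whether each event may be related to a study-mandated activity, and it names screening procedures among these.

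**Who is covered.** Section 5 states: "Adverse events are only reported for subjects enrolled in the study". It then defines the term: "Subjects are considered enrolled once they have been entered through the IVRS and have received their first dose of IP".

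**Serious events.** Section 9.2.2 covers those "that occur after signing of the informed consent through 30 days after last dose of IP" for sustained responders who never resume treatment, and otherwise up to the later of the EOT and EOS visits. Section 7.5 lists "serious adverse events that occurred after the signing of informed consent" among the screening procedures. Table 2 marks the serious-event row at screening.

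**The supplement (EU, Switzerland, Turkey).** Its Section 7.1.4 requires a baseline marrow sample, read centrally before dosing. This is either a biopsy from the year before the planned first dose, with tissue or slides available, "or a pre-treatment bone marrow biopsy and aspirate within 3 weeks prior to planned first dose of romiplostim". Children with collagen or a change to grade 3 reticulin have a further biopsy at an EOS visit 12 weeks after stopping romiplostim. The supplement adds a cohort subsection to Section 5 and lists no change to Section 9.

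**Analysis.** SAP 10.6.1 summarises treatment-emergent events recorded from the start of investigational product.

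**The concern.** The supplement adds an invasive, study-mandated procedure at two points that the reporting rules do not cover: before the first dose, and after the treatment period. The children qualify under criterion 4.1.4 with a documented platelet count of at most 30 x 10^9/L or bleeding not controlled by conventional therapy, so biopsy-site bleeding or haematoma is a foreseeable complication. An ethics committee weighing the marrow objective would want those complications counted. As written, the adverse-event tables cannot show the non-serious ones that start before dosing or after the EOS biopsy. The question about relation to screening procedures is not collected for non-serious events with pre-dose onset.

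The second issue is one of consistency. A site that reads Section 5 literally could conclude that a serious event in a consented child who is never dosed need not be reported. Three other places say that it must be.

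**Working it through.** The documents state no figure for this point, so the check sets the rules side by side.

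**Step 1. Where each kind of event goes**

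| Event | Medical record (9.1.1) | Adverse-event eCRF (9.2.1, Table 2) | SAP 10.6.1 summaries |
|---|---|---|---|
| Non-serious, new screening biopsy, onset before first dose, child later dosed | Yes | No | No, unless it worsens after dosing |
| The same, child never dosed | Yes | No | No |
| Non-serious, screening biopsy, onset after first dose | Yes | Yes | Yes |
| Non-serious, Year 1 or Year 2 biopsy while on treatment | Yes | Yes | Yes |
| Non-serious, after the 12-week EOS biopsy | Yes | No | No |

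The gap is therefore set by onset date, not by the procedure as such. It affects children who are later dosed as well as screen failures.

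**Step 2. Serious events before dosing**

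- Sections 7.5 and 9.2.2 and Table 2: reportable from consent, with no condition that the child is later dosed.
- Section 9.1.2: a serious adverse event is defined as a kind of adverse event.
- Section 5: adverse events are reported only for enrolled subjects, and enrolment requires a first dose.

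For a child who is later dosed, these agree. For a child never dosed, Section 5 read literally says no and the other three say yes. The end points in 9.2.2 (30 days after last dose, or the later of EOT and EOS) rest on a dose or visit that such a child does not have, so no stop date is given.

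**Step 3. Scale, on assumed rates**

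Inputs: N = 60, the supplement's minimum; a = share using an archived biopsy (not stated); r = share of new biopsies followed by a non-serious complication with pre-dose onset (not stated, assumed 1% to 20%).

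Expected events not collected = N x (1 - a) x r.

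| r | a = 0 | a = 0.5 |
|---|---|---|
| 1% | 60 x 0.01 = 0.6 | 0.3 |
| 5% | 60 x 0.05 = 3 | 1.5 |
| 10% | 60 x 0.10 = 6 | 3 |
| 20% | 60 x 0.20 = 12 | 6 |

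With a = 0, the chance of missing at least one event is 1 - (1 - r)^60: 45% at r = 1% and 95% at r = 5%. Screen failures who had a new biopsy would add to the counts.

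For comparison, if 60 new biopsies were followed and no pre-dose complication occurred, the exact 95% upper limit would be 1 - 0.025^(1/60) = 6.0%. Current collection cannot support a statement of that kind.

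**The case against.** Collecting non-serious events from the first dose is a deliberate and consistent choice, repeated in 9.2.1, Table 2 and SAP 10.6.1. Much biopsy harm is still visible. Section 9.1.1 requires events in the medical record. Section 7.5 sends screening physical-examination findings to the medical history or adverse-event eCRF. Section 7.4 records ITP rescue medication from screening, so a transfusion given for a biopsy bleed would leave a trace. Section 9.1.2 allows clinically important events, such as those needing an emergency visit or urgent intervention, to be classed as serious. On-treatment Year 1 and Year 2 biopsies fall inside the window.

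All of this stands and narrows the point, but none of it is systematic collection of pre-dose biopsy complications. The medical record does not feed the planned tables, and classing an event as serious is discretionary.

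On serious events, the specific rules agree with each other. The Appendix A form has boxes for onset before first dose and for relation to a procedure such as a biopsy. Section 9.2.2 also requires reporting of serious events learned of outside the period. Section 5 is the outlier, and it may have been meant for non-serious events only.

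A reader might infer three stronger things that the documents do not support:

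- That no non-serious harm from baseline biopsies can ever be captured. Onset or worsening after dosing is collected, and a new biopsy falls within 3 weeks before the planned first dose.
- That serious events in screen failures will be lost. Three passages require them; the defect is a contradictory sentence and a missing stop date.
- That biopsies are done when platelet counts are lowest. Criterion 4.1.4 gives an entry condition, not the count at biopsy.

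**Conclusion.** The point holds in a limited form. Non-serious complications of a new screening biopsy with onset before dosing, and those of the 12-week EOS biopsy, are outside the adverse-event eCRF and the planned summaries. Section 5 contradicts 7.5, 9.2.2 and Table 2 on serious events in consented children who are never dosed, and the end of reporting for them is undefined.

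The size cannot be fixed from the documents, because neither the share of archived biopsies nor a complication rate is given. Under the assumptions above (60 biopsies, all new), it is about 0.6 to 12 pre-dose events; archived biopsies lower this. The number of EOS biopsies depends on marrow findings and is not estimated here. The efficacy endpoints, the sample size and the treatment-emergent tables are not affected. The change is worth making because the procedure is invasive and study-mandated and the correction is cheap.

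**What to change.** 1. In the supplement, amend 9.2.1 and Tables 2 and 2b so that non-serious events related to a study-mandated marrow biopsy or aspirate are collected from signing of consent, and also after the EOS biopsy, with a stated follow-up period. Limit this to marrow procedures; extending it to every study procedure would bring in blood draws for all of the approximately 200 children for little gain. Collection of other events from the first dose stays as it is.
2. Present events outside the present window in a separate listing, so that the treatment-emergent summaries in SAP 10.6.1 do not change.
3. Reword Section 5 along these lines: *Non-serious adverse events, other than those related to a study-mandated marrow biopsy or aspirate, are reported only for enrolled subjects. Serious adverse events are reported for all consented subjects.*
4. In 9.2.2, state when serious-event reporting ends for a consented subject who is never dosed.

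Cost: protocol and supplement wording, one short eCRF page, one listing and a few more eCRF entries.

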Bleeding was the only event of interest observed on study. When adjusted for exposure duration, the rate of bleeding was 7.3 events per 100 subjects-weeks in the romiplostim arm and 11.9 events per 100 subject-weeks in the placebo arm. Bleeding events were mostly mild and occurred early in the treatment period when platelet counts were $< 50 \times 10^9/L$. No bleeding adverse events were considered to be serious or treatment related.

Product: Romiplostim
Protocol Number: 20101221
Date: 15 August 2014

Page 18 of 69

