6.2.2 Dosage Adjustments: Delays or Rules for Withholding Investigational Product

Each subject's dose will be adjusted based on platelet counts. The rules outlined in [Table 1](#) describe how the adjustments are to be made during the study.

Table 1. Dose Adjustment Rules

Platelet count (x 10 ⁹ /L)	Investigational Product Dose Adjustment Rule ^a
< 50 ^b	Increase dose by 1 µg/kg each week (to a maximum of 10 µg/kg)
50 to 200 ^b	Dose remains constant
> 200 to < 400 ^{b,c}	After the platelet count remains in this range for 2 consecutive weeks, dose reduce by 1 µg/kg
≥ 400 ^{b,c,d}	Withhold the dose and dose reduce by 1 µg/kg on the next scheduled day of dosing when platelet count falls < 200 x 10 ⁹ /L

^a If the platelet count is elevated in response to the initiation or increase in dose of another ITP medication, then the same dose of IP should be administered when the platelet count is ≤ 200 x 10⁹/L.

^b Romiplostim may be used with other therapies for ITP (refer to Section 6.4). If the subject's platelet count is ≥ 50 x 10⁹/L, other ITP therapies may be reduced or discontinued.

^c If the current dose is 1 µg/kg and a dose reduction is required, the dose will be withheld until the platelet count falls to < 50 x 10⁹/L. Once the platelet count is < 50 x 10⁹/L, dosing will resume at a dose of 1 µg/kg using the dose adjustment rules above.

^d If platelet count ≥ 400 x 10⁹/L is due to rescue medications, it is at the discretion of the investigator to reduce the dose by 1 µg/kg.

In situations in which withholding a romiplostim dose results in a rapid drop in platelet count, an alternate dosing schedule may be authorized on a case-by-case basis with the approval of an Amgen medical monitor.

The subject's body weight will be reassessed every 12 weeks. Subsequent doses of romiplostim will be re-calculated using the new weight. If the volume (mL or µL) of IP will be increasing due to an increase in body weight > 2.5 kg, the unit dose (µg/kg) of IP should not be increased until a platelet count has decreased to < 50 x 10⁹/L requiring an increase in dose.

All doses of romiplostim will be administered on a weekly basis. Should a subject miss a dose of romiplostim, the dose can be taken within 1 day of the scheduled date of administration. Should the subject miss a dose outside of the 1 day window, the subject will continue with the subsequent dose at the next scheduled weekly date.

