7.7 End of Treatment Visit (EOT)

All subjects will complete an EOT visit. For subjects who complete the 36-month treatment period and who have been off romiplostim and other medications for ITP (concomitant or rescue) for 4 weeks or more, the EOT visit will be the final study visit and will occur after the completion of the 36-month treatment period. For subjects ending the 36-month treatment period for non-response or other reasons while still receiving romiplostim, this visit will be 1 week after the last administration of romiplostim.

The following assessments will be completed at the EOT visit:

- physical exam, including vital signs
- documentation of concomitant and rescue medications
- adverse event reporting
- central lab CBC with differential and blood chemistry
- local lab platelet counts
- collection of blood samples for anti-romiplostim antibodies
- local lab peripheral blood smear
- local lab urine or serum pregnancy test for female subjects of child-bearing potential (defined as having first menses)

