7.8 End of Study Visit (EOS)

Four weeks after the last dose of romiplostim for subjects who end the 36-month treatment period for non-response or other reasons while still receiving romiplostim will have an EOS visit.

The following assessments will be completed at the EOS visit:

- local lab platelet count
- serious adverse event reporting
- documentation of concomitant and rescue medications

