10.3.2.2 Safety Endpoints

The exposure-adjusted incidence rates as well as subject incidence rates of adverse events will be summarized by system organ class and by preferred term according to the MedDRA dictionary. Exposure-adjusted rate is defined as total number of events divided by time of duration when subjects were under observation. The summary includes all treatment-emergent adverse events recorded from the start of IP on this study, or any worsening of conditions present at baseline before dosing in this study. This summary for adverse events will be performed for the following categories

- all adverse events
- romiplostim-related adverse events
- serious adverse events
- adverse events leading to withdrawal from the study
- adverse events of interest (hemorrhage events, etc.)

In addition, incidence and exposure-adjusted rates of adverse events by period may also be explored.

Subject listings for all adverse events, serious adverse events, and adverse events leading to withdrawal from the study will be provided.

The incidence and percentage of subjects who develop anti-romiplostim antibodies (binding and if positive, neutralizing) at any time will be tabulated.

Summary statistics will be provided for blood chemistry and CBC at each time point. Shift tables between the worst post-baseline and baseline values will be provided (based on the National Cancer Institute CTCAE, version 3.0).

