#### 6. Definitions

| Term                                      | Definition/Explanation   |
|---|--|
| End of study for individual subject (EOS) | Defined as the last day that protocol-specified procedures are conducted for an individual subject   |
| End of treatment (EOT)                    | Defined as the last assessment for the protocol-specified treatment phase of the study for an individual subject   |
| End of study (primary completion)         | Defined as the time when the last subject is assessed or receives an intervention for the purposes of final collection of data for the primary outcome. This will occur once the last subject participating has completed the EOS visit. |
| Interactive Voice Response System (IVRS)  | Telecommunication technology that is linked to a central computer in real time as an interface to collect and process information.   |

| Term                                      | Definition/Explanation   |
|---|--|
| Study Day 1                               | Defined as the first day that romiplostim is administered to the subject   |
| Study Week 1                              | Defined as the week that the first dose of romiplostim is administered to the subject                                    |
| Study day                                 | Defined as (calendar date – first dose date) +1  |
| Study treatment period                    | Defined as the period from the date of first dose of romiplostim till the date of last dose of romiplostim plus one week |
| Treatment duration for individual subject | Defined as the (last dose date – first dose date)+7 days   |
| Baseline Platelet Count                   | The average of available platelet counts obtained at screening and pre-treatment prior to dosing.                        |
| Study baseline                            | Other than for platelet count, the baseline is defined as data immediately prior to first dose administration            |
| Platelet response                         | Defined as platelet count of $\geq 50 \times 10^9/L$ without rescue medication use for ITP in the past 4 weeks           |

Page 2 of 2

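### Non-serious adverse events, including non-serious bleeding, are not collected between EOT and EOS in children who end treatment while still on romiplostim

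*Protocol*

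**What the plan says.** Protocol 9.2.1 sets the window for non-serious adverse events: those "that occur after first dose of investigational product through the end of treatment period are reported using the applicable eCRF". For subjects who end while still receiving romiplostim, Protocol 7.7 times EOT so that "this visit will be 1 week after the last administration of romiplostim". SAP 6 closes the study treatment period at the same point: "Defined as the period from the date of first dose of romiplostim till the date of last dose of romiplostim plus one week".

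The same subjects then have an EOS visit, which Protocol 7.8 places "Four weeks after the last dose of romiplostim for subjects who end the 36-month treatment period". It lists three items: a local platelet count, "serious adverse event reporting", and concomitant and rescue medications. Protocol Table 2 agrees, since its adverse event row stops at EOT while its serious adverse event row runs on to EOS. Protocol 9.2.2 collects serious events in these subjects to the later of the two visits. Table 2b of the supplement for the EU, Switzerland and Turkey delays EOS to 12 weeks after discontinuation for subjects with collagen or a change to grade 3 reticulin.

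Protocol 10.3.2.2 and SAP 10.6.1 give hemorrhage as the only named example of an adverse event of interest. Both define the exposure-adjusted rate as events over the time subjects were under observation, and neither says when observation ends.

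**The concern.** Long-term safety is a secondary objective, adverse event incidence is a secondary endpoint, and bleeding is the event the plan singles out. Reporting of serious events may not stand in for it. On the phase 2 study, Protocol 2.4 says: "No bleeding adverse events were considered to be serious or treatment related". It adds that bleeding was mostly mild and occurred when counts were below 50 x 10^9/L.

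Low counts after romiplostim stops are foreseeable. Protocol 6.2.2 provides for situations where "withholding a romiplostim dose results in a rapid drop in platelet count". That sentence concerns doses withheld during treatment, so it supports the mechanism but does not itself fall in the gap.

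EOS therefore measures the platelet count and the rescue response but not the non-serious bleeding that would go with them. If observation time were taken to EOS, the rates for non-serious events would also include time in which no such event could be recorded.

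**Working it through.** The plan states no figure for this gap, so there is none to reproduce. The check sets the windows side by side and then illustrates the size.

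**1. Length of the gap (weeks after last dose, subjects ending on drug)**

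- Non-serious events close at EOT, week 1 (Protocol 9.2.1, 7.7, Table 2; SAP 6).
- Serious events, platelet count and rescue use run to EOS, week 4 (Protocol 9.2.2, 7.8, Table 2).
- Gap = 4 - 1 = 3 weeks.
- With the delayed EOS (supplement Table 2b): 12 - 1 = 11 weeks, ignoring visit windows.

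**2. Who passes through it**

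- In the gap: children who end while on drug. These include non-responders taken off (6.2.3), children stopped for neutralizing antibodies (6.2.2), children stopping for splenectomy (6.7), and those still dosed at 36 months (7.7, 7.8).
- Not in the gap: children who stop romiplostim with a sustained response, who stay in the 36-month treatment period on the Table 2 schedule (3.1.1, 7.6). Also completers who have been off romiplostim and other ITP medication for 4 weeks or more, for whom EOT is the last visit (7.7).

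**3. Illustrative bleeding counts**

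Events = children x gap weeks x rate per subject-week. The rates are those of Protocol 2.4, 0.073 (romiplostim) and 0.119 (placebo). The number of children is an assumption; 200 is the planned total and hence the ceiling.

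| Children in gap | Subject-weeks | At 0.073 | At 0.119 |
|---|---|---|---|
| 50 | 50 x 3 = 150 | 10.95 | 17.85 |
| 100 | 100 x 3 = 300 | 21.9 | 35.7 |
| 200 | 200 x 3 = 600 | 43.8 | 71.4 |

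For one child with a delayed EOS: 11 x 0.073 = 0.80 to 11 x 0.119 = 1.31 events.

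**4. Denominator, if observation time runs to EOS**

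Share of a child's time without non-serious collection = gap / (w + gap), where w is weeks from first dose to EOT.

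| w | 3-week gap | 11-week gap |
|---|---|---|
| 12 | 3/15 = 20% | 11/23 = 47.8% |
| 24 | 3/27 = 11.1% | 11/35 = 31.4% |
| 52 | 3/55 = 5.5% | 11/63 = 17.5% |
| 156 | 3/159 = 1.9% | 11/167 = 6.6% |

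In a pooled rate where every child has the 3-week gap, w is the mean treatment time, so early stoppers carry little weight.

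Ending the denominator at EOT has the opposite problem: serious events reported between EOT and EOS could enter the numerator without their time. With the two collection windows as written, no single end point fits both kinds of event.

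**The case against.** The strongest reply is that this is a deliberate and consistent design choice. Table 2 and Sections 7.7, 7.8 and 9.2.1 all agree, the study is descriptive, and its safety objective concerns romiplostim as a long-term treatment rather than the weeks after it. The consistency is accepted: nothing here is a drafting contradiction.

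It can also be said that bleeding leaves other traces. Serious bleeding is collected to EOS, and the serious category can take in events needing an emergency visit or urgent intervention (9.1.2). Rescue medication, which is allowed for bleeding or wet purpura (6.4), is recorded at EOS. Observed and reported events go into the medical record (9.1.1). The point about serious bleeding stands in full, so a reader who infers that all bleeding after stopping goes unrecorded would be wrong. The other traces stand only in part. Rescue records show treated cases without event, grade or relatedness, and the medical record does not feed the adverse event tables.

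The size is open to challenge too. The phase 2 rates come from 17 and 5 children over 12 weeks, with bleeding concentrated early in treatment. Carrying them to children who stop after up to 3 years is extrapolation. Some may also continue romiplostim by another route (8.2, 12.1). These objections stand, and they are why the counts are illustration only.

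**Conclusion.** The gap is real: 3 weeks without eCRF collection of non-serious adverse events for children who end while on romiplostim, and about 11 weeks for supplement subjects with the delayed EOS. It is a modest weakness that is cheap to remove. The bleeding counts (about 11-18, 22-36 or 44-71 for 50, 100 or 200 children) assume that phase 2 rates hold after stopping, and the number stopping on drug is not documented.

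Three stronger readings are tempting, and the documents do not support them.

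- That every child has the gap. Sustained responders off drug and off-therapy completers do not.
- That these are the weeks of highest bleeding risk. No section says so, and Protocol 2.4 places phase 2 bleeding early in treatment. Foreseeable risk is as far as the text goes.
- That the reported rates are diluted. This depends on an end of observation that neither document states, and for a child treated 156 weeks the share is only about 1.9% with the 3-week gap.

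Nor does the absence of serious bleeding among 22 phase 2 subjects show that none would be serious here.

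**What to change.** - Add adverse event reporting, at least for hemorrhage, to the EOS column of Table 2, to Section 7.8 (and the supplement's own text for 7.8), and to the window in Section 9.2.1.
- In Protocol 10.3.2.2 and SAP 10.6.1, state when observation ends for the exposure-adjusted rates, and make it the point at which adverse event collection ends. Once both kinds of event run to EOS in these subjects, one denominator serves both.
- Reconcile the SAP 6 treatment period (last dose plus one week) with the protocol's continued follow-up of sustained responders off drug. As worded, it would leave their off-drug time outside the treatment period although adverse events are still being reported.

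The cost is protocol and SAP text changes, a few more eCRF entries at a visit that already takes place, and a slightly higher reported adverse event count. No visit, procedure or treatment rule changes.
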